For the older potential subjects (>39 years old) who have regular but short menstrual cycles e.g. ~20 days, they may be peri-menopausal women. For women suspected to be peri-menopausal, they are instructed to come to our GCRC for a blood draw (15 ml, 1 tablespoon) on the day after the first detection of menstrual spotting/bleeding. This blood will be analyzed for estradiol and FSH to determine if they are going through menopause and if they may qualify for the remaining study.

After written consenting, the following information will be collected to determine their eligibility; some are collected soon after consent while others obtained after all baseline visits.

Subjects must be:

- a) 30 to 40 years of age with normal mammograms, free of mammographic abnormalities,
- b) have regular cycles, FSH levels ≤ 10 mU/ml and mid-luteal phase and progesterone > 8 ng/ml (to be confirmed during baseline observation period),
- c) be able to return to Galveston for scheduled study visits, and
- d) be premenopausal.

The subjects must not:

- a) use contraceptive agents, any exogenous hormones, or medications known to affect the mammographic density,
- b) be pregnant or lactating,
- c) have a previous history of breast augmentation, reduction or lifting, abnormal mammograms, or at high risk for breast cancer (history of breast cancer, first degree relative with breast cancer),
- d) on medically prescribed diets, or be willing to be randomized,
- e) be peri-menopausal, e.g. estradiol > 100 pg/ml on second day of their menstrual spotting and FSH > 20 mU/ml (to be assessed by blood tests),
- f) have a pacemakers or other permanent metal implants,
- g) have a past history of allergic reaction to soy foods,
- h) be postmenopausal, and
- i) have bra cup size greater than 38DD and no less than A [PI note: We are using digital mammography and the detector plate of GE's Senographe 2000 is too small for bra cup size larger than 38DD].

The other screening tests include a complete history (including a self-administered PHQF), and a physical examination including gynecological examination, a breast examination, and a Pap smear, a three 24 hr-food records (record the 24 hr food intake before each scheduled GCRC visit, a total of three times), one blood sample (22 ml, 1.5 tablespoon) for blood chemistries, complete blood cell counts, liver and thyroid function tests, ferritin, and lipid levels and one blood sample (15 ml if suspected to be peri-menopausal) for ovarian hormones and FSH measurement. Nipple aspiration will be performed on all subjects during these baseline visits. After the consent visit, enrolled subjects are given Harvard DAQ, PHQF, food record form with instruction, a urine jug with sodium azide and glycerol added and instruction on how to collect 12 hour urine the night before each scheduled visit, and Menstrual Flow Chart and Supplement Intake Chart with instruction on how to record these information to take home.

During each GCRC visit (screening, baseline or pill intervention), weight, height, waist, hip, blood pressure, and temperature are recorded. These measurements are part of the standard of medical care. During each GCRC visit, any major changes in dietary habits, medications, and medical

- conditions are checked and recorded. These changes may confound study outcomes and affect the continuing eligibility of subjects.
4. Screening and baseline visits. Subjects will record the first day of menstrual spotting (cycle day 1) and menstrual cycle lengths and visit GCRC on 2 cycle days of cycle days 20, 22, and 24 of two menstrual cycles. These dates of visits will be scheduled for the subjects by the staff based on the monthly report/phone calls by the study subject of the first day of menstrual bleeding. Subjects will bring back a 12-hr urine collected the night before each GCRC visit. Subjects will provide one fasting blood sample (30 ml for obtaining serum and 20 ml for isolating blood cells) during each of these visits. During every scheduled GCRC visit, the subjects will be queried if they have any major change in their dietary habit, medications, or medical conditions, and the changes, if any, will be recorded. Subjects will also bring back a 24 hr-food record describing what their food intake is for the 24 hr prior to the scheduled GCRC visit. Day 1 is the first day of menstrual bleeding. These blood samples will be analyzed for estradiol, progesterone, other steroids, and hormones. Blood cells will be analyzed for cDNA. Breast fluid secretors will also provide nipple aspirates during these GCRC visits. Attempts to aspirate fluids will also be made on non-secretors during these visits. Breast fluids will be stored and analyzed for selected steroids or hormones later. Subjects will bring back a 24-hr food record (24 hr food intake for the day before each scheduled GCRC visit) three times for each menstrual cycle. The 6 baseline blood samples are analyzed immediately after the subjects complete the baseline study for estradiol and progesterone. If they have regular cycles and if progesterone is >8 ng/ml, they will continue the pill intervention portion of the study. The subjects will be notified only if they are disqualified to continue. PI will call the to be-disqualified subjects and explain to them that their progesterone levels are lower than the cut-off to continue the study. We are expecting pill intervention to decrease progesterone levels. If their progesterone is too low to begin with, it may be very difficult to decrease it further by intervention. As to the clinical implication of a low progesterone level, the subject is advised by the PI to consult her personal physician.
 5. Subjects who satisfactorily complete above tasks including the 4 scheduled GCRC visits will have a pregnancy test and, if not pregnant, will be given a mammography, a bilateral breast MRI, and duplicate DEXA bone density tests (L2 to L4 and hip) during one of these GCRC visits. The mammogram results will be interpreted immediately as for all clinical mammography tests by a licensed radiologist. Dr. [name] (certified to interpret mammograms and breast MRI), our co-investigator will interpret the mammograms and if there are abnormalities, the subjects will be informed the test results by phone and by mail by the Radiology Staff according to the established clinical protocol in place in our Radiology Department. Specifically, the subjects will be advised to have additional diagnostic tests and be advised to consult their own physician for this follow-up. The cost of these follow-up diagnostic tests will not be the responsibility of this project. If the subjects have cancer lesions after further diagnostic tests, they will be excluded from the study. [name] will inform [name] and the PI of any abnormal test results. PI will also phone

- study subject, advise the subject to consult her personal physician, to have follow-up diagnostic tests, and to inform us the results of the diagnostic tests to determine their continuing eligibility in our study. [name] will also assess the density of these women according to the established diagnostic guideline. [name] who is certified to interpret DEXA results will interpret bone density results for this project.
6. Pregnancy test will be determined during screening and during pill intervention if menstrual cycle lengthens by 2 weeks or more, or within 48 hours prior to scheduled mammography and DEXA bone density tests.

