All procedures (mammography, MRI) and samples (fasting blood, overnight 12-hr urine, and nipple fluid) will be obtained during the mid-luteal phase of the menstrual cycle (between cycle days 20 to 24 preferably day 22) when progesterone levels peak. Subjects will record cycle day 1 (onset of menstrual spotting) throughout the study and complete a dietary habit history questionnaire (DAQ) (8) and reproductive history and general health history questionnaires (PHQF).

During each GCRC outpatient visit, subjects will bring a 12-hr overnight urine (stored in a urine jug containing sodium azide and glycerol), 24-hour food records. Menstrual cycle lengths and body weights will be recorded and fasting blood samples obtained for serum chemistries, liver and thyroid functions, lipid profiles, and steroid hormones. Breast fluid secretors will provide nipple fluid aspirates for analysis of epithelial cytology and hormones.

Baseline observations (2 menstrual cycles): There will be 3 GCRC visits per menstrual cycle for at least 2 cycles. Complete history, physical examination and a Pap smears will be obtained. Subjects who qualify will then be randomized, undergo mammography (a standard screening mammography and one extra view), bilateral breast MRI, and a bone density measurement by DEXA (L2 to L4 and hip).

Pill supplementation intervention period (24 months): Isoflavone or control pill supplements will begin on the second day of menstrual bleeding soon after the baseline observation period. Every three months (~ seasonally) subjects will visit the GCRC on day 22 of a cycle. At these visits, subjects will be provided with the assigned supplement pre-packaged for daily dose and consumption. Subjects will be randomly assigned to placebo or treatment in blocks of six to assure equal sizes of the pill group and of the sub-groups for blood sampling, using the PLAN procedure in SAS® (9).

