Soy isoflavone pills and maltodextrin placebo pills. The make-up of the isoflavones is the same as that which exists naturally in soy. We believe studying the effect of the two soy isoflavones at their naturally occurring ratio is a pre-requisite to contemplating a study that addresses the effect of different ratio or the individual isoflavone. The total amount of isoflavones in each tablet will be maintained constant through formulation. The formulation consists of, for example, 125 mg Novasoy (50 mg of total isoflavones as aglycones) or equivalent weight of placebo material, 60 mg sorbitol, 3 mg magnesium stearate, 412 mg dicalcium phosphate with a total of 600 mg per tablet. [Note: Volunteers in this study will take 2 pills (=120 mg isoflavones as aglycones) per day.] For placebo, 10-DE maltodextrin (90% weight) and RT-175 caramel color (10% by weight) will be substituted for Novasoy [Note: Volunteers will take 2 tablets per day.] The relative amount of genistein/genistin to daidzein/daidzin does vary between lots of soybeans and this variation is a natural phenomenon. This ratio for Novasoy has varied between 1.1 to 1.3 (mean \pm SD: 1.2 ± 0.1) from lot-to-lot. However, we will use only one lot of Novasoy for the entire study. Therefore, the relative amount of the two isoflavones will be constant. All subjects (both treatment and placebo) will be given required daily intake of multi-vitamin and minerals. Vitamin pill will be packaged with treatment assignment pill in container for daily dosage and consumption.

Breast density: Breast density of subjects will be determined by both mammography and bilateral breast MRI at the outpatient Radiology Clinic at UTMB. Both tests will be performed during the luteal phase, as confirmed by obtaining a blood sample on the days of the breast density tests for measuring progesterone.

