Study Population: Subjects must be 30-40 years of age and be free of mammographic abnormalities. They must be willing and able to return to Galveston for scheduled study visits. We expect to enroll the 200 subjects required for the study within 6-8 months. Women will be excluded from the study if they are on contraceptive agents, any other exogenous hormones, or medications known to affect mammographic density; are pregnant or lactating; or have a previous history of cancer, breast augmentation or reduction, abnormal mammograms, or are at high risk for breast cancer (first degree relative with breast cancer). Women who are on any medically prescribed diet, or are not willing to be randomized will be excluded. Women with pacemakers or other permanent metal implants such as IUD will be excluded from the study. During initial screening, past history of allergic reactions to foods will be acquired. If subjects have prior histories of food allergies to soy food, they will be excluded. Subjects must have regular cycles and mid-luteal phase progesterone > 8 ng/ml. Perimenopausal women with > 100 pg/ml of serum estradiol on cycle day 2 and > 20 mU/ml FSH will be excluded. Enrollment will be available to all racial groups. Pregnancy will be excluded by measuring urinary hCG (human chorionic gonadotropins) by standard clinical testing procedure.

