The subjects are given the Harvard DAQ, Personal Heath Questionnaire for Females (PHQF), and Menstrual Flow Chart and Supplement Intake Chart (MFC-DSC) to fill out. The PHQF is the standard of medical care forms to be filled out by patients visiting UTMB clinics including our GCRC, respectively. PHQF is the form used by UTMB Gynecology Clinic to collect reproductive history. The PHQF are reviewed by the physician investigators of this project as a part of history taking. Subjects can fill out these forms while at UTMB or they can take these forms home and fill out. For Spanish speaking only subjects, our Spanish speaking nurse from our GCRC or the Spanish speaking staff translate the questionnaires or forms and collect information by interview. The subjects also take urine jug, food records form home to fill out. The subjects are instructed on how to keep track of their cycle information. On the first day of their menstrual spotting (cycle day 1), they call our office to give us this date. From this date, we calculate when their luteal phase (post-ovulatory phase, the latter half of the menstrual cycle, usually cycle days 14 to 28) will be and days 20, 22 and 24 of their cycles. The

appointment is made for them to come in on these dates to have fasting blood draws and nipple fluid aspiration, to turn in their 12-hour urine collection and food records.

During this inform consent visit, the subjects are told that they may be removed from the study after certain diagnostic tests have been performed, for example, low progesterone level, abnormal mammograms, abnormal blood chemistries that cannot be resolved and if they are going through menopause.

The inform consent is performed by the authorized Study Coordinators or the PI. The PI visits and interacts with the study subjects frequently during their scheduled GCRC visits for clarifying study procedures, study purposes, and their concerns.

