 13. After completing 12 months of pill supplement, subjects will complete another Harvard DAQ (recall food intake frequency for the past 12 months of pill intervention) and will be given a pregnancy test, followed by a mammography, a breast MRI, and a DEXA bone density test.

14. Subjects will continue consumption of the assigned pill, have the 1-day visit to GCRC for blood draw and other study procedures once every three months (e.g. repeat steps 6 to 14) for another 12 months.
15. Pregnancy test will be performed whenever cycle length increases by >30% of each subject's usual length. Pregnancy test will also be performed no longer than 48 hrs prior to taking mammography and DEXA tests to ensure that pregnant women are not exposed to radiation. Gynecological examination including Pap smear will be done at the end of the study.
16. Transvaginal probe ultrasonography and endometrial biopsies will be performed when medically indicated, for example, if amenorrhea develops. This will be performed by Dr. [name].

Risk and Benefit Assessment:

The soy isoflavone are currently available as pills over-the-counter and are found in soy foods sold to the public. We will use isoflavone tablets provided by the Archer Daniel Midland Co., which we have used in the past several years for several preliminary studies. These isoflavones are isolated by repeated alcohol extractions of soy protein isolates or soy protein concentrates (different processing). Alcohol is then removed by evaporation and the residues used for tablet formulation. In this way, the make-up of the isoflavones is the same as that which exists naturally in soy. These pills are sold as nutritional products over-the-counter to the public. The placebo pills contain maltodextrin, a carbohydrate, and should have no biological effect at the dose, 150 mg, to be given to the subjects.

Populations consuming soy have reduced risk of breast and endometrial cancers, reduced mammographic density, and reduced hip fracture rate. The FDA has approved a health claim regarding soy consumption and risk reduction for cardiovascular diseases. There are no other known risks from soy isoflavones from population-based studies, as soy products are commonly consumed in many countries. However, adverse effects have not been previously looked for carefully, so it is possible that there are unknown risks.

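### The pre-scan pregnancy test is timed too early in the cycle to support the stated assurance that no pregnant woman is exposed to radiation, as far as conceptions in the scan cycle are concerned

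*Combined protocol and SAP*

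**What the plan says.** The assurance is in Clinical Procedures, step 15, which has the test done "no longer than 48 hrs prior to taking mammography and DEXA tests to ensure that pregnant women are not exposed to radiation". Step 6 repeats the window: "within 48 hours prior to scheduled mammography and DEXA bone density tests". Neither step names the specimen. The type of test comes from Study Population: "Pregnancy will be excluded by measuring urinary hCG (human chorionic gonadotropins) by standard clinical testing procedure".

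The scan dates come from Experimental Design and Methods, where mammography, MRI and samples "will be obtained during the mid-luteal phase of the menstrual cycle (between cycle days 20 to 24 preferably day 22". The Breast density section makes clear that the scans are meant to be post-ovulatory: "Both tests will be performed during the luteal phase, as confirmed by obtaining a blood sample on the days of the breast density tests". DEXA is not named in that timing sentence, but steps 5 and 13 and the flow chart put it together with mammography. The Recruitment section dates the "luteal phase (post-ovulatory phase, the latter half of the menstrual cycle, usually cycle days 14 to 28".

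The women are aged 30 to 40, have regular cycles and must have mid-luteal progesterone above 8 ng/ml. By the eligibility list they must not "use contraceptive agents, any exogenous hormones, or medications known to affect the mammographic density". Outside the scan visits and screening, a pregnancy test is triggered only by a lengthened cycle: by 2 weeks or more in step 6, by more than 30% of the usual length in step 15.

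**The concern.** A pregnancy test gives no information about a conception that is still too recent to register. This plan places its scans after ovulation by design and tests at most two days before them. If a woman conceives in the same cycle, the test may well be negative when she is scanned. The protocol nevertheless presents the test as the safeguard that keeps pregnant women from radiation, and the lengthened-cycle tests can act only after the scan.

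What is at stake is a stated safety property. The women are ovulating and users of contraceptive agents are excluded, so conception on study is possible, and the Remuneration section itself foresees removal for pregnancy. If participants are given the same assurance, they are told something that the schedule does not deliver.

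**Working it through.** **Inputs from the protocol**
- Scan day S: 20 to 24, preferably 22 (Experimental Design and Methods).
- Test lead L: 0 to 48 hours, taken as 0, 1 or 2 days (Clinical Procedures, steps 6 and 15).
- Ovulation day O: about 14, from the start of the luteal phase (Recruitment).

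**Assumption, not in the protocol**
- hCG becomes detectable T days after ovulation, with T between 8 and 15.

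**Step 1: when the test falls.** Days after ovulation at the test = S − L − O.
- Earliest: 20 − 2 − 14 = 4.
- Latest: 24 − 0 − 14 = 10.
- Day-22 scan: 22 − 2 − 14 = 6 to 22 − 0 − 14 = 8.

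**Step 2: comparison with the detection time.** Five scan days and three leads give 15 permitted combinations. A combination is too early if S − L − O is below T.

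| Assumed T (days after ovulation) | At or past detection | Too early |
|---|---|---|
| 8 | 6 of 15 | 9 of 15 |
| 9 | 3 of 15 | 12 of 15 |
| 10 | 1 of 15 | 14 of 15 |
| 11 to 15 | 0 of 15 | 15 of 15 |

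At the preferred day 22, only a same-day test reaches T = 8, and no permitted test reaches T = 9 or more. These are counts of permitted timings, not proportions of women.

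**Step 3: cycle length.** Taking ovulation as cycle length minus 14 (a further assumption), the test falls this many days after ovulation:
- 25-day cycle (O = 11): 7 to 13
- 26-day cycle (O = 12): 6 to 12
- 28-day cycle (O = 14): 4 to 10
- 30-day cycle (O = 16): 2 to 8
- 32-day cycle (O = 18): 0 to 6

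Short cycles narrow the gap and long cycles widen it. In a 25-day cycle with T = 8, only the day-20 scan tested two days ahead (20 − 2 − 11 = 7) is too early. In a 30-day cycle with T = 8, only the day-24 scan tested the same day (24 − 0 − 16 = 8) is not.

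**Step 4: the other tests.** For a usual cycle of 28 days, a lengthening of more than 30% is reached after 28 × 1.3 = 36.4 days, and one of 2 weeks at 28 + 14 = 42 days. The latest permitted scan is on day 24, so these tests come at least 36.4 − 24 = 12.4 or 42 − 24 = 18 days after it. They can reveal a conception in the scan cycle but cannot prevent the exposure.

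**The case against.** The decisive premise is external. The protocol gives no detection time, and without one its passages do not conflict. At the lower end of the assumed range 6 of 15 timings would already detect a conception, and in short cycles most would. This stands as a limit on how firmly the point can be put: the test is too early for most or all timings under the stated assumptions, not too early as a matter of documented fact. It does not rescue the assurance, because a promise to ensure something fails if even a substantial minority of permitted timings cannot deliver it, and at the preferred scan day almost none can.

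The Study Population sentence applies an exclusion criterion at entry. A reader might take it as a promise that every scan cycle is free of pregnancy, but its context does not support that. The assurance is in step 15. That the pre-scan test is a urine test is itself inferred from Study Population.

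A reader might also infer that these women have no means of avoiding pregnancy. "Women will be excluded from the study if they are on contraceptive agents, any other exogenous hormones" sets contraceptive agents beside hormones, and IUDs are barred as metal implants. Nothing visible bars barrier methods or sterilisation. Consent pages and some other pages were not available for this review, so advice on avoiding pregnancy may exist there and its absence cannot be asserted.

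Finally, the dose is low by the protocol's own account: Risk and Benefit Assessment likens mammography plus DEXA to one flight across the United States. That bears on the seriousness of the gap, not on whether the assurance is accurate.

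**Conclusion.** The point holds for conceptions in the scan cycle. On the protocol's own calendar the test falls about 4 to 10 days after ovulation, and for T from 8 to 15 days between 9 and 15 of the 15 permitted timings are too early. This rests on ovulation at day 14, the assumed detection range, and urinary hCG as the pre-scan test. The test keeps its value for a pregnancy begun in an earlier cycle.

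Two stronger readings are not supported. One is that a given number of women will be irradiated while pregnant: the documents give no conception rate, so no count can be derived. The other is that the density or progesterone data are contaminated. Pills start on the second day of menstrual bleeding after baseline, so a woman with a continuing pregnancy from the baseline scan cycle would not start as planned, and the main analysis requires a post-baseline density measure. A pregnancy begun around the month-12 scan would come to light through the lengthened-cycle test and is grounds for removal. Nothing in the documents shows that density is altered so early. Any effect on the results is expected to be small, and sample size and power are untouched. This is a correction to a safety statement.

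**What to change.** Reconcile the luteal-phase scan timing in Experimental Design and Methods with the test rules and the assurance in Clinical Procedures, steps 6 and 15, and with the test named in Study Population. The two lengthened-cycle triggers in steps 6 and 15 differ and should be aligned in the same revision. Restate the assurance as what a negative test at that time can show, chiefly that there is no pregnancy from an earlier cycle. If the participant information carries the same assurance, align it. The clinical investigators should decide how the scan-cycle gap is covered; no clinical rule is proposed here.

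Optionally, use the cycle-day-1 dates that women already report to flag month-12 and month-24 scans later found to fall in a conception cycle. The last scan closes the study, so its flag needs one further report of menses. Very early losses would still be missed.

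The cost is a wording amendment, submitted to the IRB and GCRC as the protocol requires, and, if the option is taken, one derived variable and one extra contact per woman. The safety statement becomes less reassuring but accurate.
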